## Data Collection and Statistical Analysis

Three-dimensional structural images are obtained from a T1-weighted sequence; (sagittal direction, 0.7 in-plane resolution) as well as functional images collected with simultaneous UDS (axial echo-planar, TR = 3,000ms, 4.0mm slice thickness, 3.38mm in-plane resolution). AFNI software will be used for analysis. Structural and functional images will be registered and motion-corrected. Patients with rapid motion (> 4.5mm) will be excluded from analysis. Voxel activation will be identified at “initiation of voiding” which is signaled by patient’s right hand. Significant differentially-activated voxels will be identified under the generalized linear model. Group level analysis will be performed by transforming data into Talairach space, and significantly activated/deactivated voxels will be identified using a Student’s T-test or a non-parametric test if indicated. We will use SPSS (v19.0) to perform statistical analysis of clinical data (i.e. demographic, UDS data). FC analysis will be performed using CONN, a functional connectivity toolbox for MATLAB, Version 15a, which utilizes the statistical parametric mapping MATLAB toolbox. fMRI images acquired during the voiding task together with their corresponding anatomical datasets will be processed using the default- Montreal Neurological Institute (MNI) preprocessing option to enable group analysis in MNI space. A region-based connectivity analysis will be performed for each patient group based on ROIs. FC will be quantified by T-values for a p-value < 0.05 (two-sided, FDR-corrected). Diffusion Tensor Imaging (DTI) images will be acquired (32 directions, one B0 image) using the standard MRI pulse sequence available on the Siemens 3Tesla or 7 Tesla MRI scanner. The software packages TackVis (version 0.6.0.1) and the Diffusion Toolkit (version 0.6.3, trackvis.org) will be used to calculate and extract selected white matter tracts of interest. This software also enables calculating FA and MD values for the segmented WMTs.

**Power Analysis:** fMRI studies suggest that approximately 12 subjects are required to achieve 80% power at the single voxel level for typical activations, while accounting for intra-and inter-subject variability. Most fMRI studies, evaluating bladder function have included 8-12 subjects. For this proposed study, we account for 10% exclusions due to movement artifact and anticipate 13 patients for groups 1 and 2, with total of N=26.

(Recruitment and scanning is already completed for Aims 1 and 2, data analysis is pending funding). Aim 3 is a small pilot feasibility study and we propose N=8.

**Limitations of the study and alternative strategies:** The primary strength of this study is the simultaneous neuroimaging and UDS platform which includes the voiding or attempt to void phase. However, limitations do exist: voiding dysfunction is heterogeneous and dynamic and variations within studies may exist. Our patient population represents only a subset of a larger and more complex group and may have inter and intra-subject variability. Although patients with MS are generally accustomed to UDS and MRIs, combined UDS/fMRI may create anxiety and non-physiologic state. Furthermore, voiding supine may pose a challenge to many individuals who can void spontaneously while seated. The repetition of the filling and voiding task four times is an attempt to provide a high enough level of signal to evaluate the fMRI data. This provides a rich dataset that can be analyzed to infer information about the brain at initiation of voiding. Additionally, by preselecting our ROIs and WMTs we increase our specificity; however we may miss other important brain centers/pathways.

Direct comparisons between the current TRPMS prototype that we plan to use and a commercially used conventional TMS coil show that the maximum voltage induced in an inductor by the former (12 - 30 V/m) is about 6% of the maximum machine output of the latter (200 - 500 V/m). Although this lower voltage has added advantages of portability, multi-site stimulation capability, and significantly lower side effects such as heat, seizure activity, or headaches, it may raise a concern of not being strong enough to have an effect in our patients. Alternatively we may add to the stimulated targets or consider selecting only one region and use the commercially available TMS for our next trial.

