# **Brain Targets in Patients with Bladder Emptying Difficulties**

**NCT03574610**

**Document Date: January 24, 2020**

## Research Strategy: Supraspinal Targets in Neurogenic Voiding Dysfunction

### 1. SIGNIFICANCE

Voiding dysfunction (VD) is a morbid and costly urological condition characterized by intermittent, fluctuating, or absent flow of urine. VD may lead to incomplete bladder emptying or urinary retention, urinary tract infections, sepsis, bladder or kidney stones, and permanent renal failure and can be present in patients with or without neurologic disorders.

- *Currently the only available therapies for VD include indwelling bladder catheters or intermittent selfcatheterizations.*

Catheterization is a burden, in general, and even more so in neuropathic patients, in whom lower extremity spasms, compromised hand dexterity, or visual disturbances, may be present. The cost and morbid side effects (hematuria, pain, trauma, strictures, and infections), associated with catheterizations, urge us to look into alternate ***therapeutic targets for VD, possibly beyond the bladder, such as the brain*** (where bladder and urethral control centers are located).

The human lower urinary tract has two functions: storage and voiding. This study will concentrate on supraspinal (brain) areas controlling the delicate and complex neural circulatory (the “switch”) from storage of urine to initiation of voiding. Normal voluntary voiding is controlled by suprapontine centers in the brain, allowing the pontine micturition center to trigger (switch on) the voiding reflex. VD occurs if the detrusor muscle cannot maintain effective contractions (e.g., *detrusor underactivity*), if the urethra fails to relax and lower urethral resistance, or if there is failure in synchronizing these actions leading to detrusor sphincter dyssynergia (DSD) in subset of neuropathic patients. ***Almost all patients with DSD are dependent on catheterization and are at much higher risk for autonomic dysreflexia, recurrent urinary tract infections, and renal insufficiency.***

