## OBJECTIVES/ SPECIFIC AIMS/ HYPOTHESES

**A priori selected grey matter Regions of Interest for aim 1:** Based on our preliminary data and the summary of literature outlined in table 1, we propose the following *a priori* selected ROIs for the **cortical and deep grey matter and nuclei for aim 1**: Inferior frontal and precentral gyrus, thalamus, PAG, and pons. **A priori selected white matter tracts (WMT) for aim 2:** Since MS lesions affect the white matter mainly, it is prudent to evaluate the WMT involved in bladder function in this patient population. Two WMTs are particularly important in proper function of the bladder: Anterior thalamic radiation (ATR) and Superior longitudinal fasciculus (SLF).

Clinical and UDS data will be used to categorize female MS patients with stable disease into two groups. The standardization of terminology by the International Continence Society does not provide clear definition for VD, however we propose the following based on expert opinion. Group 1: MS patients with VD (patients who perform self-catheterization or have a postvoid residual of urine  $\geq 20\%$  Maximum Cystometric Capacity); and Group 2: MS patients without VD (patients who void spontaneously and their postvoid residual of urine  $< 40\%$  Maximum Cystometric Capacity). Patients in Group 1 will be further subdivided into patients with DSD (Group 1a) versus without DSD (Group 1b). DSD is defined as increased EMG activity  $\geq 20\%$  during detrusor contraction (voiding) in the absence of valsalva maneuvers on UDS.

We **hypothesize** that female MS patients with VD have a distinct pattern of brain activation and connectivity at “initiation of voiding” and targeted cortical modulation may be feasible and lead to improved voiding.

**Specific Aim 1: Activation patterns of the grey matter ROIs are different among female MS subjects with VD, specifically those with DSD.** We will determine the distinct activation patterns by:

- Assessing Blood Oxygen Level Dependent (BOLD) signal and functional connectivity (FC) patterns in the ROI's at “initiation of voiding” in Groups 1a, 1b, and 2.
- Comparing BOLD signals and FC patterns in Group 1 versus 2, and specifically Group 1a versus 1b.

**Specific Aim 2: Damage to preselected WMT in female MS patients provides an independent predictive measure for VD.** We will use diffusion tensor imaging and our established algorithm of measurement to:

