## Description of interventions

**Subject Evaluations:** Each patient will undergo a detailed history and physical examination with the following assessments: Demographic Form, American Urological Association Symptom Score (AUASS), Neurogenic

Bladder Symptom Score (NBSS), MRI Safety Screening Questionnaire, Hospital Anxiety and Depression Scale, and Expanded Disability Status Scale. AUASS and NBSS both include questions regarding the voiding phase and are validated in neurogenic patients. Postvoid residual urine, urinalysis, urine culture, and pregnancy (if applicable) will be assessed prior to the MRI scan. A clinical UDS will be performed within 10 years prior to the neuroimaging scan. Consent will be signed during the first visit. High density Electromyography (EMG) will be performed at the beginning of the first and the last sessions of TRPMS treatment however this is an optional testing and patients can refuse to participate in the EMG testing. Patients from Group 1 who participate in the TRPMS will undergo a repeat fMRI scanning following the completion of the therapy. In addition their symptoms will be assessed with repeat UDS and validated questionnaires.

After their post TRPMS Intervention Fmri visit, subjects will return to the clinic to complete 4 months (+/- 1 month) and 12 months (+/-1 month) follow up visits. At these follow-up visits, they will completing validated questionnaires, uroflow testing and PVR scan.

**Simultaneous UDS/fMRI:** Double lumen 7 French MRI-compatible catheters are placed in the bladder and rectum. Either 3T or 7 T full body MRI scanner with standard 12 channel head coil is used. Instructions to communicate using right hand signals representing “strong desire to void” and “voiding” are given. In order to keep our noise-to-signal ratio low, all stimulators including any extra visual stimuli and the UDS machine are removed from the MRI room. Filling and voiding cycles are repeated up to 4 times in each patient. If the patient is unable to void, then the bladder will be drained passively.

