**Transcranial Rotating Permanent Magnet Stimulator (Aim 3 only):** We will use the data obtained in Aim 1 to further identify superficial cortical targets for intervention in each patient with voiding dysfunction and we will construct an individualized therapeutic cap to deliver repeated 100 – 500 ms stimuli at 0.02 Hz for 40 min each week day for 2 weeks (based on our preliminary TRPMS data in other neurological disorders). As discussed in the Innovation section of this proposal, TRPMS is safe, precisely programmable, inexpensive, and can modulate multiple areas of the brain at the same time, making it an ideal modality for our proposal.

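### Because a right-hand signal marks the voiding event, left lateral precentral activation cannot be attributed to voiding in within-group maps, and the plan has no step to handle it

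*Combined protocol and SAP*

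**What the plan says.** The section Data Collection and Statistical Analysis defines the modelled event as the start of voiding, "which is signaled by patient’s right hand". Under Description of interventions, the simultaneous UDS/fMRI paragraph gives the same hand two tasks: "Instructions to communicate using right hand signals representing “strong desire to void” and “voiding” are given". Filling and voiding are repeated up to four times per patient, and functional images are taken every 3 s.

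The a priori grey matter regions for Aim 1, in the objectives section, are "Inferior frontal and precentral gyrus, thalamus, PAG, and pons". Two of the five are cortical, and neither hemisphere nor sub-region is given for the precentral gyrus. Primary endpoint (a) is BOLD signal and functional connectivity (FC) in these regions at the start of voiding in MS patients.

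On modelling, the plan says only "Significant differentially-activated voxels will be identified under the generalized linear model". It names no hand-movement regressor, hand-only run, motor localizer or contrast with the strong-desire signal. The limitations paragraph does not mention the hand signal.

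For Aim 3, the stimulator paragraph states: "We will use the data obtained in Aim 1 to further identify superficial cortical targets for intervention in each patient with voiding dysfunction". The closing bullet of the Innovation section says that regions found in Aims 1 and 2 will join Table 1 to individualize the targets.

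**The concern.** The event that defines the map is also a motor act. By standard anatomy, which the documents do not discuss, moving the right hand engages left lateral precentral cortex. That lies inside a primary-endpoint region as the plan defines it. A response there at the start of voiding could come from voiding, from the hand, or from both, and nothing in the plan separates them.

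Two uses of the result are exposed. A within-group map subtracts no comparison group, so the hand response stays in it. And a left lateral precentral region reported from Aim 1 could be handed to target selection as a voiding region.

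**Working it through.** The plan gives no figure for this point, so there is none to reproduce. What can be checked is how far a model can separate the hand response from the voiding response.

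**Inputs from the plan:** one image every 3 s; up to four cycles; event timed by the hand signal; two right-hand signals per cycle.

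**Assumptions, not in the plan:** double-gamma haemodynamic response; 300 s cycles; 1 s hand movement; voiding modelled as 1, 10 or 20 s; strong-desire signal 30 s before voiding.

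**Step 1: the event as written.** If the hand signal sets the event time and both are modelled as brief, the two regressors are identical (r = 1.00). The whole hand response loads on the voiding estimate.

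**Step 2: voiding onset and hand movement differ by a lag, both brief.** The variance inflation factor is VIF = 1/(1 − r²).

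| Lag (s) | r (about) | VIF |
|---|---|---|
| 0.5 | 0.99 | about 35 (from r = 0.986) |
| 1 | 0.94 | 1/(1 − 0.884) = 8.6 |
| 2 | 0.80 | 1/(1 − 0.64) = 2.8 |
| 3 | 0.60 | 1/(1 − 0.36) = 1.6 |
| 5 | 0.23 | 1/(1 − 0.053) = 1.06 |

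These values move a little with where events fall on the 3 s grid (for example 0.93 to 0.96 at 1 s). Using two cycles rather than four leaves them unchanged, so repetition does not remove the overlap.

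**Step 3: voiding modelled as a longer block.** The share of the hand peak that loads on voiding when the hand is not modelled is:
- 10 s block, signal 0 to 3 s after onset: about 45 to 75%.
- 20 s block, signal at onset: about 12 to 18%, depending on timings.
- 20 s block, signal up to 3 s after onset: rising to about 33%.

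The plan does not say which duration will be used.

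**Step 4: which added regressor helps.** Take a voxel that responds only to the hand.
- *A separate strong-desire regressor* absorbs only the earlier movement. In a brief-event simulation with strong desire 15 to 60 s before voiding, the loading on voiding was 92 to 98% without it and 100% with it. It removes nothing.
- *One hand regressor covering both signals* removes the loading if both movements evoke the same response. With coincident brief events, the hand regressor is the voiding regressor plus a nearly uncorrelated copy of equal variance. So r² is about 1/2 and VIF about 1/(1 − 1/2) = 2 (computed: 1.96). Across the scenarios with lags of 0 to 3 s and blocks of 1 to 20 s, VIF runs from 1.03 to 1.96.

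**Step 5: what a hemisphere split would leave.** Table 1 has four rows labelled precentral: left lateral (-44, 1, 28), right superomedial (2, -32, 66), left superomedial (-6, -26, 74) and right (54, -4, 6). Only the first lies in the exposed area.

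**The case against.** The strongest reply is that Group 1 v 2, 1a v 1b and before v after stimulation are contrasts, and an equal hand response cancels in them. That stands. A reader might infer that these contrasts are biased, because the Significance section mentions "compromised hand dexterity" and because patients who cannot void may give no voiding signal. The documents do not show this. The dexterity remark concerns the burden of catheterization in neuropathic patients generally; both groups have stable MS, and severe debilitating MS is excluded. Patients void or attempt to void, and a missing signal is first a missing-event problem. Unequal hand responses or signalling are possible, but not shown.

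A reader might also infer that the left precentral row in Table 1 is a hand artefact. It comes from healthy subjects on this platform and is labelled Brodmann area 6; nothing identifies it as hand cortex. The platform's two MS rows are inferior frontal, and its reported DSD findings do not include left precentral cortex.

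A third inference is that each cap is built from that patient's own contaminated map. Aim 1 is a retrospective cohort and Aim 3 is a pilot of 8; the documents do not say which scan feeds each cap.

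Finally, the overlap depends on the event model, and with a 20 s block it is modest. That stands too, but the plan does not commit to such a model. None of these replies protects a within-group map.

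**Conclusion.** The point holds in a limited form. Under the plan as written, left lateral precentral activation at the start of voiding cannot be attributed to voiding in the within-group results for primary endpoint (a), and it can enter the regions passed to Aim 3. The overlap ranges from complete (brief events timed by the signal) to about 12 to 18% of the hand peak (20 s block, signal at onset). The size of the hand response itself is unknown, so no bias in BOLD units can be stated.

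The conclusion rests on standard motor anatomy and the assumed timings above. It concerns mainly one part of one hemisphere in one of five regions; right precentral, inferior frontal, periaqueductal and pontine results should be less affected. It does not establish that between-group or before-and-after comparisons are wrong. The plan should be amended, but this does not undermine the study as a whole.

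**What to change.** Amend Data Collection and Statistical Analysis before the Aim 1 analysis, which the power section describes as pending:

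1. Report the precentral region by hemisphere. Use the right and midline/superomedial parts as the Aim 1 precentral endpoint. Label left lateral precentral activation as unconfirmed for voiding, and carry that label forward when Aim 1 regions are passed to target selection. Three of the four precentral rows in Table 1 stay within the endpoint.
2. Where signal times are available, add to the first-level model one hand-movement regressor covering both the strong-desire and the voiding signals, not a separate strong-desire regressor. Report it as a sensitivity analysis limited to left precentral cortex, and state the assumption that both movements evoke the same response. The protocol says patients are told to signal; it does not say that signal times were logged, so step 2 is conditional.

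Masking out voxels that respond at both signals is not a good substitute. It would select on the same voiding data that define the endpoint, and could remove the left superomedial site in Table 1.

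The cost is wording and a small amount of analysis, with no new scans. The downside is that a true left lateral precentral voiding focus would be treated as unconfirmed, and the sensitivity analysis loses some precision there (variance up to about doubled, from VIF of about 2).

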### 3. APPROACH

#### Preliminary Data over the past four years

[figure not shown]
a three-dimensional augmented reality (AR) device in HC during repetitive voiding. The network under investigation was found to consist of two large sub-networks, one in the frontal lobe and one that connected sensory regions with deeper brain structures, including the PMC. This data will serve as our HC for this proposal.

**MS patients:** We have evaluated twenty-seven MS patients with neurogenic lower urinary tract dysfunction using our established fMRI/UDS platform. Our analyses described, for the first time, brain regions activated at initiation of voiding in female

Figure 4. BOLD signals at initiation of voiding. A, HCs B, MS showing higher signals in regions with warmer colors. C, subtraction image between MS and HCs.

**Healthy Controls (HC):** Our established fMRI/UDS platform demonstrated activation of brain regions of cerebellum, thalamus, caudate, lentiform nucleus, supplementary motor area, postcentral gyrus, left superior frontal gyrus, anterior and posterior cingulate gyrus and insula, as well as other brain structures such as the pons at the time of “initiation of voiding” HC, figure 3. We also have established an algorithm visualization and evaluation of neuroimaging data

Figure 3. Average fMRI activation maps with concurrent UDS tracings. Asterisk denote “initiation of voiding” in the event-related analysis of the fMRI data in HC.

[figure not shown]

MS patients (Figure 4).

**MS patients with DSD:** Our data on a subgroup analysis of MS patients with DSD (n=4), showed statistically significant greater activation in the right middle frontal gyrus, right medial frontal gyrus, right cingulate gyrus, right caudate nucleus, and brainstem at “initiation of voiding”.

**Changes in brain following intradetrusor injection of OnabotulinumtoxinA (IDBTX-A):** fMRI/UDS results from our recent study examining the impact of IDBTX-A in MS with urinary urgency (N=12) demonstrated that activation increased in specific brain regions associated with the sensation and process of urinary urgency six weeks post therapy (Figure 5). This is the first study of its kind to evaluate the possible sensory effects of IDBTX-A in humans. These preliminary results have been submitted to the 2018 national Urology and Neurology meeting.

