## Endpoints

### Primary Endpoint

- a) BOLD signal intensity and FC pattern in *a priori selected* ROIs at “initiation of voiding” in MS patients.
- b) BOLD and FC pattern changes following TRPMS.

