### Secondary Endpoints

- a) FA and MD of ATR and SLF white matter tracts in Groups 1 and 2.
- b) Clinical scores: UDS parameters, urinary symptom scores, surveys at baseline and following TRPMS.
- c) BOLD signal characteristics and FC patterns in ROIs in patients with versus without DSD.

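### Aim 1 promises between-group comparisons, but the analysis section names no between-group FC test and leaves the BOLD group test without an ROI limit, threshold, correction or one-/two-sample form

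*Combined protocol and SAP*

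**What the plan says.** **Objective.** Under Objectives/Specific Aims/Hypotheses, Aim 1 has two bullets. The first assesses BOLD and FC in Groups 1a, 1b and 2. The second is "Comparing BOLD signals and FC patterns in Group 1 versus 2, and specifically Group 1a versus 1b". The stated hypothesis is that MS patients with voiding dysfunction show a distinct pattern of activation and connectivity. The a priori grey-matter ROIs are "Inferior frontal and precentral gyrus, thalamus, PAG, and pons", which makes five.

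**Endpoints.** Primary endpoint (a) is "BOLD signal intensity and FC pattern in" the preselected ROIs at initiation of voiding in MS patients. Secondary endpoint (c) is "BOLD signal characteristics and FC patterns in ROIs in patients with versus without DSD".

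**Analysis.** Data Collection and Statistical Analysis gives one FC method: a region-based analysis "performed for each patient group based on ROIs. FC will be quantified by T-values for a p-value < 0.05 (two-sided, FDR-corrected". For BOLD, a generalized linear model is followed at group level by this rule: "significantly activated/deactivated voxels will be identified using a Student’s T-test or a non-parametric test if indicated". The FDR statement is attached to FC only.

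**Sample size and status.** Power Analysis gives 13 patients per group (N=26), and says that scanning for Aims 1 and 2 is complete and analysis is awaiting funding. The limitations text that follows credits preselection of ROIs with greater specificity.

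**Earlier results.** Preliminary Data shows a BOLD figure for MS patients and healthy controls at initiation of voiding ("C, subtraction image between MS and HCs"). It also states: "Our data on a subgroup analysis of MS patients with DSD (n=4), showed statistically significant greater activation". Table 1 lists voiding-phase coordinates from MS patients.

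**The concern.** Testing each group's connectivity against zero answers whether a link is present in that group. Aim 1's second bullet asks whether the link differs between groups. These are different null hypotheses, and results for the first do not settle the second. With small groups, the same true connectivity can easily pass the threshold in one group and miss it in the other.

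The BOLD gap is of another kind. The restriction to five ROIs is what the plan relies on for specificity, yet the sentence describing the group test works on voxels and does not carry that restriction over. Without a threshold, a correction or a one-/two-sample form, several quite different analyses would all comply with the text. Because the scans already exist, those choices could be made with the data in hand.

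**Working it through.** **1. Aims against methods.**

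| Aim 1 task | Method stated |
|---|---|
| Describe FC in each group | Per-group ROI analysis, two-sided p<0.05, FDR |
| Compare FC, 1 v 2 and 1a v 1b | None |
| Describe BOLD in each group | Voxelwise t or non-parametric test; no alpha, correction or ROI limit |
| Compare BOLD, 1 v 2 and 1a v 1b | The same sentence; one- or two-sample form not stated |

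The mention of group analysis in MNI space describes preprocessing and is not a contrast. No other section fills the empty cell.

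**2. The plan's own figure.** Power Analysis starts from about 12 subjects and allows 10% for motion. 12/0.9 = 13.3 and 12 × 1.1 = 13.2, so 13 per group and N=26 reproduce to rounding. The base of 12 cannot be reproduced, because no effect size, SD, alpha or contrast is given.

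**3. Why per-group significance is not a comparison.** Suppose a link has the same true strength in both groups and each within-group test has power p. The chance that exactly one group is significant is 2p(1−p): 2 × 0.8 × 0.2 = 32% at p=0.8, and 50% at p=0.5.

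**4. Illustration over all links.** This models a procedure that the plan does not state, namely comparing the groups' lists of significant links. Assumptions: identical true FC in both groups; 13 v 13; ten links (5 × 4/2 pairs of ROIs) correlated at 0.5; the same standardised strength d on every link; 5% FDR within each group; 20,000 simulated studies per value of d.

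| d | At least one link significant in only one group |
|---|---|
| 0 | 9% |
| 0.3 | 36% |
| 0.6 | 87% |
| 0.8 | 90% |
| 1.0 | 63% |
| 1.2 | 26% |

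A direct two-sample Welch test with FDR across the ten links gives at least one false difference in about 4% of studies throughout. The documents give no d or correlation, so the table shows the mechanism and does not estimate this trial's error rate.

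**5. What a direct test can detect.** Two-sided, two-sample t with n per group, df = 2n−2 and noncentrality d/√(2/n), solved for 80% power:

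| n per group | alpha 0.05 | alpha 0.05/5 = 0.01 (first Holm step, five ROIs) |
|---|---|---|
| 13 | d = 1.145 | d = 1.441 |
| 12 | d = 1.197 | d = 1.511 |

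At 13 v 13 with equal SDs, the 95% CI half-width is 2.064 × √(2/13) = 0.81 SD.

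**6. Group 1a v 1b.** The planned split is not given. Assume 4 v 9, from the preliminary DSD n of 4 and 13 − 4 = 9. With equal SDs the median Welch 95% half-width is about 1.4 SD. If the smaller group's SD is 1.5 or 2 times as large, the half-width is about 2.0 or 2.7 SDs of the larger group. In those two cases a pooled-variance interval covers only 91% and 87%, while Welch holds about 94%.

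No false-positive figure is given for BOLD, because the plan states no threshold from which to compute one.

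**The case against.** The best defence is that this is one missing step and not a wrong method. The per-group FC analysis matches Aim 1's first bullet, the comparisons are named in the aim, CONN is already the chosen software, and the ROI restriction is stated in the aims, the endpoints and the limitations. All of that stands. What remains is that naming a comparison as an objective does not specify its test, and that the BOLD sentence leaves open choices that change the answer. The small-pilot label does not excuse it, since the plan applies that label to Aim 3 only.

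A reader might infer four stronger things that the documents do not support:

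- **That the investigators will compare lists of significant links.** The plan does not say so, and the MS-minus-control BOLD image shows that the team has made a direct subtraction before. That image is neither an FC test nor a Group 1 v 2 test, so it does not close the gap either.
- **That primary endpoint (a) itself requires a group contrast.** As worded, it names none. The requirement comes from Aim 1's second bullet and the hypothesis.
- **That a chance Aim 1 difference passes straight into Aim 3.** Aim 1 regions are added to the Table 1 literature regions, and targets are then individualised to superficial cortex. Of the five ROIs, only the inferior frontal and precentral gyri are cortical.
- **That fixing the SAP now would be clean prespecification.** Preliminary Data and Table 1 already report initiation-of-voiding BOLD results from MS patients, including a DSD subgroup, and Aims 1 and 2 reuse a previously completed cohort.

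**Conclusion.** The point holds as a gap in the analysis section that should be fixed. Followed as written, the plan produces no test of the FC difference that Aim 1 promises, and its BOLD group test is not tied to the five ROIs or to any error rate. This conclusion comes from the text alone and needs no assumed number.

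The sizes are conditional. The detectable differences of about 1.15 (uncorrected) and 1.44 (first Holm step) assume 13 analysable patients per group, normal data and equal variances. The half-width of about 1.4 SD for 1a v 1b assumes a 4 v 9 split with equal SDs. The discordance percentages illustrate a procedure that the plan does not state, and the conclusion does not rest on them.

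**What to change.** Amend Data Collection and Statistical Analysis as follows.

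1. **FC.** Add a two-sample, second-level Group 1 v 2 contrast in CONN on per-patient Fisher-z ROI-to-ROI values, two-sided and FDR-corrected across all connections. Report mean differences with 95% CIs. Keep the per-group T-values as description.
2. **BOLD.** Make the Group 1 v 2 test a two-sample comparison of per-patient ROI-mean signal, Holm-corrected over the five a priori ROIs. A small-volume-corrected voxel test within those ROIs would also close the gap. Label whole-brain maps exploratory, at a stated corrected threshold.
3. **Group 1a v 1b.** Use the same two-sample form without assuming equal variances. Lead with estimates and 95% CIs, and state that precision is very low if the DSD group is small.
4. **Timing.** Set these choices before the Group 1 v 2 analysis is run. Disclose which initiation-of-voiding BOLD results from MS patients, including the DSD subgroup, have already been seen.

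The cost is SAP wording and a contrast in software already named; no new data are needed. The price is fewer nominally significant findings and openly low power. Only large group differences, of the size shown above, would be detected reliably.
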